#### 8.2 AE/SAE Intensity and Relationship Assignment

#### - AE/SAE Intensity

The investigator must rate the intensity for all AEs that occur during the study, following "Guidance for Industry: Toxicity Grading Scale for Healthy Adult and Adolescent Volunteers Enrolled in Preventive Vaccine Clinical Trials" (Appendix 1), issued by United States Food and Drug Administration in September 2007. The definition of Grade 5 (death) was added to this grading system as it was not defined in the guidance.

The toxicity grade of adverse events will be rated according to the following definition by the investigator when AEs are not listed in the US FDA Guidance (Appendix 1) applied in this study:

- Grade 1 (Mild): No interference with activity
- Grade 2 (Moderate):
   Some interference with activity not requiring medical intervention
- Grade 3 (Severe):
   Prevents daily activity and requires medical intervention
- Grade 4 (Life threatening):
   Emergency room visit or hospitalization
- Grade 5 (Death)

Note: The definitions of Grade 1 to Grade 4 follow "Guidance for Industry: Toxicity Grading Scale for Healthy Adult and Adolescent Volunteers Enrolled in Preventive Vaccine Clinical Trials" issued by United States Food and Drug Administration in September 2007 (Appendix 1). The definition of Grade 5 (death) was added to this grading system as it was not defined in the guidance (Section 8.2 and Appendix 1).

#### - AE/SAE Relationship Assessment

The investigator will be asked to assess all AEs with respect to their causal relationship to the study drug according to the following classification:

## Definitely Related

There is clear evidence to suggest a causal relationship, and other possible contributing factors can be ruled out. The clinical event, including an abnormal laboratory test result, occurs in a plausible time relationship to study agent/intervention administration and cannot be explained by concurrent disease or other drugs or chemicals. The response to withdrawal of the study agent/intervention (dechallenge) should be clinically plausible. The event must be pharmacologically or phenomenologically definitive, with use of a satisfactory rechallenge procedure if necessary.

## Probably Related

There is evidence to suggest a causal relationship, and the influence of other factors is unlikely. The clinical event, including an abnormal laboratory test result, occurs within a reasonable time sequence to administration of the study agent/intervention, is unlikely to be attributed to concurrent disease or other drugs or chemicals, and follows a clinically reasonable response on withdrawal (dechallenge). Rechallenge information is not required to fulfill this definition.

## Possibly Related

There is some evidence to suggest a causal relationship (e.g., the event occurred within a reasonable time after administration of the trial medication). However, the influence of other factors may have contributed to the event (e.g., the volunteer's clinical condition, other concomitant events). Although an adverse drug event may rate only as "possible" soon after discovery, it can be flagged as requiring more information and later be upgraded to probable or certain as appropriate.

## Unlikely

A clinical event, including an abnormal laboratory test result, whose temporal relationship to study agent/intervention administration makes a causal relationship improbable (e.g., the event did not occur within a reasonable time after administration of the trial medication) and in which other drugs or chemicals or underlying disease provides plausible explanations (e.g., the volunteer's clinical condition, other concomitant treatments).

## Not related

The AE is completely independent of study agent/intervention administration, and/or evidence exists that the event is definitely related to another etiology. There must be an alternative, definitive etiology documented by the clinician Expected Events Related to Disease Process: Provide explicit definitions of the Study ProtocolConfidentialCareseng 1370 for Healthy VolunteersVersion: 5.0(Protocol Number: Careseng 1370-01)Date: 18Sep2020type(s), grade(s), and duration(s) of adverse event(s) that will be considereddisease related.

#### 8.3 Collecting, Recording and Reporting of Adverse Events

8.3.1 Collecting and Reporting of AE

AEs may be volunteered spontaneously by the study volunteer, discovered as a result of general questioning by the study staff, or determined by physical examination. All AEs will be recorded on the eCRF. For all AEs, the investigator must pursue and obtain adequate information both to determine the outcome of the AE and to assess whether it meets the criteria for classification as a serious AE requiring immediate notification. Follow-up of the AE, even after the date of study drug discontinuation, is required if the AE persists. The study volunteer will be followed until the event resolves or stabilizes at a level acceptable to the investigator.

8.3.2 Reporting of AE

Serious, alarming and/or unusual adverse events must be reported to the Sponsor/CRO contact within 24 hours of the investigator's knowledge of the event. Any event requiring hospitalization (or prolongation of hospitalization) that occurs during the course of a volunteer's participation in a clinical study must be reported as a serious adverse event, except hospitalizations for the following:

- Social reasons in absence of an adverse event
- Surgery or procedure planned before entry into the study (must be documented in the eCRF)

The investigator is responsible to communicate details of medical emergencies in trial volunteers to the Ethics Committee. Sponsor is responsible to inform the events to the regulatory authorities.

Fatal or life-threatening, unexpected ADRs should be notified to Taiwan National ADR Reporting Center by sponsor/CRO as soon as possible, but no later than 7 calendar days and a complete report should be followed 8 additional calendar days. This report must include an assessment of the importance and implication of the findings and/or previous experience on the same or similar medical products. Serious, unexpected ADRs that are not fatal or life-threatening must be filed as soon as possible but no later than 15 calendar days.

Adverse events observed during the study will be coded using Medical Dictionary for Regulatory Activities (MedDRA) and will be reported by System/Organ/Class classified in MedDRA as appropriate. The toxicity grade of adverse events will be rated according to "Guidance for Industry: Toxicity Grading Scale for Healthy Adult and Adolescent Volunteers Enrolled in Preventive Vaccine Clinical Trials" defined in Section 8.2 and Appendix 1.

The version of MedDRA employed will be agreed by the sponsor and remains unchanged throughout the study.

#### 9. DATA ANALYSIS

#### 9.1 Data Quality Assurance

Electronic CRFs will be provided for the recording and collection of volunteer data. All eCRFs will be completed following eCRF completion guide after the volunteer's visit. Corrections to data on the eCRFs will be documented or traced. The investigator will review eCRFs to indicate that, to his/her knowledge, they are complete and accurate. If further changes are made after this, the investigator will need to again sign the investigator signature page. Designated source documents will be signed and dated by the appropriate study personnel.

#### 9.2 Clinical Data Management

The investigator must agree to complete and maintain source documents and eCRFs for each volunteer participating in the study or by his/her designees.

The sponsor/CRO will be responsible for the processing and quality control of the data. Data management will be carried out as described in the sponsor/CRO's standard operating procedures (SOPs) for clinical studies.

The handling of data, including data quality control, will comply with regulatory guidelines and the sponsor/CRO's SOPs as well as provisions of the study-specific data management plan.

#### 10. SAMPLE SIZE AND STATISTICAL METHODS

#### **10.1** Determination of Sample Size

Planned 4 cohorts of up to 6 evaluable healthy volunteers in design of traditional 3+3 paradigm with three candidate dose levels, the number of evaluable healthy volunteers will be up to 24. Around 29 eligible healthy volunteers will be recruited to complete up to 24 evaluable healthy volunteers.

Note: A volunteer is considered evaluable if he/she

1. receives any Careseng 1370, and

2. experiences DLT OR completes DLT observation period with at least 80% of study drug compliance and has exposed to Careseng 1370 for at least 4 days (level A, B and C), OR completes DLT observation period with 100% of study drug compliance (level D).

#### 10.2 Statistical and Analytical Plans

10.2.1 Analysis Population

The following populations are defined for statistical analysis.

#### Intent-to-treat (ITT) population:

- Volunteers receive any Careseng 1370

Demographic analysis, safety evaluation and pharmacokinetic analysis will be performed on the ITT population. Decision of the MTD will be made based on DLT observation of evaluable subjects.

10.2.2 Statistical analysis

Baseline characteristics, including demographic data such as gender, age, etc., will be presented using descriptive statistics and displayed by dose level (levels A to D). Additionally, descriptive statistics will be provided for all of the endpoints by dose level. Frequency table will be provided for categorical data, while mean, standard deviation, maximum, minimum, median, interquartile range (IQR), and 95% two-sided confidence interval (for data change from baseline) will be calculated for continuous measurements.

#### Safety Analyses

Adverse events observed after signing informed consent form till exit from study will be coded using Medical Dictionary for Regulatory Activities (MedDRA) using the version agreed by sponsor and will be reported by dose level by System/Organ/Class and Preferred Terms classified in MedDRA as appropriate. The toxicity grade of adverse events will be rated according to definition in Section 8.2. Findings in physical examinations will be displayed for each individual system. Changes from pre-dosing laboratory test results, body weight, EKG and vital signs to applicable post-dosing visits will be analyzed by descriptive statistics and (if applicable) will be presented by transition table for normality (normal, clinically not significant, clinically significant). Findings in 12-Lead EKG and X-ray will be presented by description.

10.2.3 Interim Analyses

There is no planned interim analysis for this study.

10.2.4 Missing Data

Missing data will be treated as missing. No missing data imputation will be employed.

#### 11. ETHICAL CONSIDERATIONS

#### 11.1 Informed Consent

Informed consent is a process that is initiated prior to the individual's agreeing to participate in the study and continuing throughout the individual's study participation. Extensive discussion of risks and possible benefits of this therapy will be provided to the participants and their families.

Consent forms will be IRB approved and the participant will be asked to read and review the document. Upon reviewing the document, the investigator will explain the research study to the participant and answer any questions that may arise. The participants will sign the informed consent document prior to any procedures being done specifically for the study. The participants should have sufficient opportunity to discuss the study and process the information in the consent process prior to agreeing to participate. The participants may withdraw consent at any time throughout the course of the trial. A copy of the informed consent document will be given to the participants for their records. The rights and welfare of the participants will be protected by emphasizing to them that the quality of their medical care will not be adversely affected if they decline to participate in this study.

#### 11.2 IRB and Regulatory Review

This protocol and the associated informed consent documents must be submitted to the IRB and health authority for review and approval. The study will not be initiated until the IRB and health authority provide written approval of the aforementioned documents and until approval documents have been obtained by the Principal Investigator and sponsor or CRO.

No changes from the final approved protocol will be initiated without the health authority's and IRB/EC's prior written approval or favorable opinion of a written amendment, except when necessary to eliminate immediate hazards to the study participants or when the change involves only logistics or administration. Any significant deviation from the protocol when no approved amendment exists will be regarded as a protocol violation, and will be addressed as such during the reporting of the study.

#### 11.3 Confidentiality of Data and Volunteer Records

Include procedures for maintaining participant confidentiality, any special data security requirements, and record retention per the sponsor's requirements.

Participant confidentiality is strictly held in trust by the participating investigators, their staff, and the sponsor(s) and their agents. This confidentiality is extended to cover testing of biological samples and genetic tests in addition to the clinical information relating to participating volunteers.

The study protocol, documentation, data and all other information generated will be held in strict confidence. No information concerning the study or the data will be released to any unauthorized third party, without prior written approval of the sponsor.

The study monitor or other authorized representatives of the sponsor may inspect all documents and records required to be maintained by the Investigator, including but not limited to, medical records (office, clinic or hospital) and pharmacy records for the participants in this study. The clinical study site will permit access to such records.

The information provided by sponsor in this protocol and the associated Clinical Investigator's Brochure and the data generated by this clinical study are to be considered as confidential property of sponsor.

## 11.4 Conflict of Interest Policy

The independence of this study from any actual or perceived influence, such as by the pharmaceutical industry, is critical. Therefore, any actual conflict of interest of persons who have a role in the design, conduct, analysis, publication, or any aspect of this trial will be disclosed and managed. Furthermore, persons who have a perceived conflict of interest will be required to have such conflicts managed in a way that is appropriate to their participation in the design and conduct of this trial.

#### **12. PUBLICATIONS**

The data and information associated with this study may be used by sponsor now and in the future for the purposes of presentation, publication at discretion of sponsor or for submission to regulatory authority. In addition, relative to the release of any proprietary information, sponsor reserves the right of prior review of any publication or presentation of data from this study.

In signing this protocol, the investigator agrees to the release of the data from this study and acknowledges the above publication policy.

#### **13. RETENTION OF TRIAL DOCUMENTS**

Records for all participants, including CRFs, all source documentation (containing evidence to study eligibility, history and physical findings, laboratory data, results of consultations, etc.) as well as IRB records and other regulatory documentation should be retained by the PI in a secure storage facility. The records should be accessible for inspection and copying by authorized authorities.

All study documentation at the clinical site and sponsor records will be archived in accordance with International Council for Harmonisation (ICH) Good Clinical Practice (GCP), applicable regulations, the sponsor's quality standards and Standard Operation Procedures (SOP)s. Study records should not be destroyed without prior written agreement between sponsor or CRO and the study investigator.

## 14. PROTOCOL AMENDMENT HISTORY

The major amendments in protocols up to current version are provided in the following table.

Version	Date	Description of Major Changes	Brief Rationale
1.0	14SEP2018	NA	NA
		Add PK blood sampling	To explore PK profiles of marker ingredient
		Add 24-hour 12-Lead EKG monitoring	To ensure safety of volunteers
1.1	24JAN2019	Add laboratory test items: aPTT, PT, and INR	To ensure safety of volunteers
		Change dosing period from 21 days to 5 days	Five days for collecting safety profiles in healthy volunteers are sufficient
		Correct definition of severity of AE	Original definition is not for healthy volunteers
		Adjust PK sampling time points and	Based on the PK profile of marker
		revise the schedule of assessments	ingredient, PPD
		Extend the safety follow-up period,	Per TFDA's comment
		and add follow-up visits at Day 15 and	
		Day 22 to monitor the long term safety	Den TED A's comment
		subjects is changed to 5 days	Per IFDA's comment
12	21MAY2019	Prohibit herbal supplement and	Per TEDA's comment
1.4	21101112019	medicinal food to avoid interfering PK	
		analysis	
		Extend the wash-out period to 2 weeks	Per TFDA's comment
		in Exclusion Criterion 3	
		Add exclusion criterion 14: Plan to	To avoid subject receiving surgery
		receive surgery from the Screening	during the trial for safety concerns
		visit until the Final visit	
		Duration for observing DLT changed	Per TFDA's comment
		Delete Dose Level D (4 sachets) and	To avoid Enjicalin (CaHPO 4 )
		adjust number of volunteers to enroll	overdose
		Add 0.5 and 72 hour (on Day 8) PK	To expand range of PK time points
		sampling time points	
		Prohibit phosphorous supplement,	To avoid Ca or P overdose
		calcium supplement, or food rich in	
		calcium during the study, and avoid	
2.0	10ПП.2019	food very rich in phosphorous	
2.0	103012017	Add exclusion criterion 15: Known or	Per CDE consultation
		suspected hypersensitivity to any	
		component of Careseng 13/0,	
		active and the second s	
		P188 Fujicalin and ginseng flavor	
		Add section for conflict of interests	For ethical concerns
		Prohibited therapy will not lead to	For statistical concerns
		being excluded from PP population or	
		withdrawal	

		(Protocol Number: Careseng 1370	D-01) Date: 18Sep2020
Version	Date	Description of Major Changes	Brief Rationale
		Increase EKG exam frequency on Day 1 and 5	Per TFDA's comment
2.1	08NOV2019	Alteration of the principle investigator and the corresponding information. One night extension of planned hospitalization	Request by the sponsor
		Change of DLT observation period as Day 1 to Day 10	Request by the DSMB to clarify the definition of DLT
		Revision of the definition for MTD	Typo to be corrected
		Addition of special scenarios in dose escalation/de-escalation scheme for DSMB review	Granted by the DSMB
		Clarification for the definition of evaluable subjects	Request by the DSMB
		Requirement of fasting on Visit 7	For the requirement of lab tests
3.0	08APR2020	Additional immunology test on Day 2 and Day 22	Request by the sponsor
5.0	00/11/12/02/0	Additional cytokines included for immunology test: CD16 and CD56	Request by the DSMB
		Revision of withdrawal criteria # 7 for study drug compliance	Request by the DSMB to be consistent with the study drug compliance
		Revision of the schedule for Visit 10 as Day 12 $(\pm 2)$	Request by the DSMB to clarify the DLT observation period
		Revision of concomitant therapy # 5: redefinition of food restriction in high calcium and provision of a calcium- restricted diet plan	Request by the DSMB to re-define the restriction for low-calcium diet
		Definition of pre-dose and post-dose for this study	Clarification of time points for PK blood sampling
4.0	10AUG2020	Re-definition of PK blood sampling time points and additional time points for PK blood sampling of Dose level B and C	Requested by the sponsor for PK analysis
		Additional description to clarify which measurements require fasting	Clear statement for fasting required measurements
		Addition of 1 lower dose cohort (level	Consideration of unexpected drug
		D), and the corresponding information	effects on human body for safety
5.0	18SEP2020	Re-definition of pre-dose and pre-dose PK blood sampling	Corresponding change in response to the addition of 1 lower dose cohort (level D)
		Addition of detailed information for results of immunology	Clear statement for the presentation of immunology results

# **Appendix 1**

# Guidance for Industry Toxicity Grading Scale for Healthy Adult and Adolescent Volunteers Enrolled in Preventive Vaccine Clinical Trials

1.1 Visit Adjustment

Visit 11 is final visit or early withdrawal visit, refer to 14.3 for detail of visit adjustment

1.2 Analysis Populations

According to the protocol, only Intent-to-treat (ITT) population was defined for analyses of primary and secondary endpoints.

Section 10.2.1 Analysis Population: Intent-to-treat (ITT) population:

- Volunteers receive any Careseng 1370

For maximal tolerated dose (MTD) determination, a MTD-Evaluable Population is defined as below according to protocol section 3.1 "Volunteers Enrollment" on DLT analysis.

MTD-Evaluable Population:

- 1. A subset of ITT population
- 2. Experiences DLT OR completes DLT observation period with at least 80% of study drug compliance and has exposed to Careseng 1370 for at least 4 days (level A, B, and C), OR completes DLT observation period with 100% of study drug compliance (level D).

1.3 Treatment Compliance

Treatment compliance is defined as below in protocol section 5.6:

Volunteer's compliance will be assessed by the following formula:	
# of sachets of study drug actually administered	- × 100%
Total # of sachets of study drug assigned at that level	- × 100%

The parameters of compliance calculation are not well-defined in the protocol. The formula to derive treatment compliance and relevant parameters are adjusted as below:

```
Treatment Compliance = # of sachets of study drug actually administered

Dose Level [Sachet/Day] × Treatment Duration × 100%

[Days]
```

• Treatment Duration [Days] = the last dosing date - the first dosing date + 1.

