# of sachets of study drug actually administered Total # of sachets of study drug assigned at that level × 100%

#### 6. STUDY MEASUREMENTS

#### 6.1 Eligibility

Eligibility should be thoroughly checked by the investigators at Screening visit and Day 1 visit.

If a volunteer is a screen failure, a minimal set of screen failure information is required to ensure transparent reporting of screen failure subjects, to meet the regulatory authority requirement and to respond to queries from regulatory authorities and IRBs/IECs. Minimal information includes demographics, screen failure details, concomitant medication, and any serious adverse event.

Re-screening for volunteer's eligibility will be allowed if the volunteer is willing to participate in the study and one of the following conditions meets:

- If a volunteer consents to participate and meets the eligibility criteria but a delay occurs in starting to participate in due to certain change in situation such that some measurement relevant to eligibility became invalid owing to the delay
- If the cause of screen failure has now resolved or adequately treated such that volunteer's conditions have now stabilized
- If there is an alternative manner to indicate that the volunteer may be suitable.

In these situations,

- A new eCRF will be used
- A new Screening number will be assigned to the person
- The person will be marked as having been re-screened on both the eCRF and the source document.
- The old eCRF will be completed as fully as possible following eCRF completion guide and data on the old eCRF is not copied to the new eCRF.
- The volunteer needs to sign a new ICF as part of the screening procedure.

It is not appropriate to re-screen a volunteer if he/she has previously failed to meet the eligibility criteria and no further changes or treatments have been able to indicate that the volunteer may be suitable.

Volunteer may be re-tested/measured for procedures relevant to causes of screen failure if investigator considers such causes can be resolved soon.

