1.4 Pharmacokinetic Analysis

Pharmacokinetic parameters will be analyzed by Mithra Biotechnology Inc. All pharmacokinetic parameters data will be provided to sponsor directly, no data handling, data listing nor statistical analysis on such data will be done by A2 Healthcare.

- 2.2 Endpoints
 - 2.2.2 Secondary endpoints
 - 2 Pharmacokinetic parameters of marker ingredient in Careseng 1370, 20(S)-protopanaxadiol (PPD) and its metabolites

Careseng 1370 for Healthy Volunteers

3 Protocol Versions and Protocol Amendments

The first subject was enrolled on 14AUG2020, and the last subject is expected to be dismissed on MAR2022. Amendments relevant to important statistical-related changes are summarized in table below, and Table/Figure/Listing programming will be based on the latest version of protocol.

Summary of important statistical-related changes for protocol version V4.0
Additional time points for PK blood sampling for Dose level B and C

Summary of important statistical-related changes for protocol version V5.0

Addition of 1 lower dose cohort (level D), and the corresponding information

Version 1.0, 08-SEP-2022 Protocol No.: Careseng 1370-01

Careseng 1370 for Healthy Volunteers

4 Mock-up Tables and Figures

The Mock-up "TABLES and FIGURES" is planned according to ICH E3, in which relevant CSR section is 14. The words shadowed below are to be adjusted or repeated upon real data, or just for notification.

Columns {Label, Dose Level} will be included in the table with the analyzed population specified. In the mock table below, only the Label with one dose level column were presented to show the descriptive/inferential statistics to be displayed in the final tabulation.

Version 1.0, 08-SEP-2022 Protocol No.: Careseng 1370-01 Confidential Page 5 of 20

Careseng 1370 for Healthy Volunteers

Instructions and Abbreviations:

(1) Site ID [C]:

Site ID	Full Name	
1	Taipei Medical University Hospital (TMUH)	

(2) Dose Level:

- A (1 sachet/day): Careseng 1370 1 sachet before breakfast for consecutive 5 days
- B (2 sachets/day): Careseng 1370 1 sachet before breakfast and 1 sachet before lunch for consecutive 5 days
- C (3 sachets/day): Careseng 1370 1 sachet before breakfast and 2 sachets before lunch for consecutive 5 days
- D (1 sachet/day): Careseng 1370 1 sachet before breakfast on 1st, 3rd and 5th days (modified cohort)

(3) Population

- Intention-to-Treat (ITT) Population:
 - Volunteers receive any Careseng 1370

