- Maximum Tolerated Dose (MTD)-Evaluable Population:
 - 1. A subset of ITT population
 - 2. Experiences DLT OR with at least 80% of study drug compliance and has exposed to Careseng 1370 for at least 4 days

(4) For Visit Name (in Tables and Figures) and Visit Code (in Subject Data Listing):

Visit No.	Visit Description	Visit Day	Visit Name	Visit Code
1	Visit 1 Screening Visit	-14 ∼ -1	Visit 1 (Screening)	V01
2	Visit 2 Hospitalization: Day -1 to Day 1	1	Visit 2 (Day 1)	V02D01
3	Visit 3 Discharge: Day 2	2	Visit 3 (Day 2)	V03D02
4	Visit 4: Day 3	3	Visit 4 (Day 3)	V04D03
5	Visit 5: Day 4	4	Visit 5 (Day 4)	V05D04
6	Visit 6 Hospitalization: Day 4 to Day 5	5	Visit 6 (Day 5)	V06D05
7	Visit 7 Discharge: Day 6 (24±2 hrs post-last dose)	6	Visit 7 (Day 6)	V07D06
8	Visit 8 Follow-up Visit: Day 7 (48±2 hrs post-last dose)	7	Visit 8 (Day 7)	V08D07
9	Visit 9 Follow-up Visit: Day 8 (72±2 hrs post-last dose)	8	Visit 9 (Day 8)	V09D08
10	Visit 10 Follow-up Visit: Day 12±2	10 ~ 14	Visit 10 (Day 12)	V10D12
11	Visit 11 Final Visit (Day 22±2, within 3 days after withdrawal)	22	Visit 11 (Day 22)	V11D22
-	Unscheduled Visit	-	-	V□□.□

(5) Full term for 'Protocol Deviation Code':

Code	Full Term
<to added="" be="" data="" final="" in="" real="" tabulation="" upon=""></to>	

(6) For clinical relevance

CS: abnormal and clinically significant LLN: lower limit of normal range NCS: abnormal but not clinically significant ULN: upper limit of normal range

(7) For Transition of Clinical Relevance

Relieved CS (Medical History or Adverse Event) at baseline to Normal / NCS at

visit.

Unchanged Including Normal at baseline to NCS at visit, NCS at baseline to Normal

at visit.

Worsened (Medical History) Normal / NCS at baseline to CS (Medical History) at visit

Worsened (Adverse Event) Normal / NCS / CS (Medical History) at baseline to CS (Adverse Event)

at visit

Version 1.0, 08-SEP-2022 Confidential
Protocol No.: Careseng 1370-01 Page 6 of 20 A2 Healthcare Taiwan Co.

Careseng 1370 for Healthy Volunteers

(8) Abbreviations of statistics

N: number of non-missing values Missing: number of missing values

Mean: mean of values

SD: standard deviation of values Q1: 25% quartile of values Q3: 75% quartile of values

Median: median of values

IQR: inter-quartile-range (IQR=Q3-Q1)

Min: minimum of values Max: maximum of values CI: confidence interval

Version 1.0, 08-SEP-2022 C Protocol No.: Careseng 1370-01 P

Careseng 1370 for Healthy Volunteers

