14.1.6 Study Drug Administration, Compliance and Exposure

Population: Intent-to-Treat Population

Characteristics	Dose Level
.Total IP Administration [sachets],	
Treatment Duration [days]	
Treatment Compliance [%],	
Mean Daily Dose [sachet/day]	
n (Missing)	XXX
Mean (SD)	XXX (XXX)
Median (IQR)	XXX (XXX)
Q1~Q3	XXX~XXX
Min~Max	XXX~XXX
. Treatment Compliance	
n (Missing)	XXX (XXX)
<60%	XXX (XXX.X%)
60 ~ <80%	XXX (XXX.X%)
80 ~ <100%	XXX (XXX.X%)
100 ~ <120%	XXX (XXX.X%)
≥120%	XXX (XXX.X%)

- Treatment Duration [days] = the last dosing date the first dosing date + 1.
- Treatment Compliance [%] = Total IP Administration [sachets] / Dose Level [sachet/day] / Treatment Duration [days] * 100%
- Mean Daily Dose [sachet/day] = Total IP Administration [sachets] / Treatment Duration [days]

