14.3.1.1 Treatment Emergent AE - Summary

Population: Intent-to-Treat Population / MTD-Evaluable Population

Characteristics [Event#:Subj#]	Treatment	
Repeat Population: Intent-to-Treat Population, MTD-	Evaluable Population	
n	XXX	
Subjects with AE	XXX : XXX (XXX.X%)	
Subjects with Treatment-Related AE	XXX : XXX (XXX.X%)	
Subjects with DLT	XXX : XXX (XXX.X%)	
Subjects with Grade ≥3 AE	XXX : XXX (XXX.X%)	
Subjects with Grade ≥3 Treatment-Related AE	XXX : XXX (XXX.X%)	
Subjects with AE Leading to Action Taken	XXX : XXX (XXX.X%)	
Subjects with AE Leading to Drug withdrawn	XXX : XXX (XXX.X%)	
Subjects with SAE	XXX : XXX (XXX.X%)	
Subjects with Death SAE	XXX : XXX (XXX.X%)	
Subjects with SUSAR	XXX : XXX (XXX.X%)	
Subjects with Death SUSAR	XXX: XXX (XXX.X%)	

Subject with multiple events are counted as one incidence.

Treatment-Related is defined as Definitely Related, Probable Related, or Possibly Related

Programmer's Notes:

Repeat Population only when the two populations are not identical

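### The SAP's compliance formula scores a fully adherent level D volunteer at 60%, so no fully adherent DLT-free volunteer at that level can be MTD-Evaluable

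*SAP*

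**What the plan says.** Protocol 5.6 defines compliance as sachets actually taken divided by "Total # of sachets of study drug assigned at that level". SAP 1.3 calls the parameters of that formula poorly defined and substitutes the labelled daily dose times treatment duration, with "Treatment Duration [Days] = the last dosing date - the first dosing date + 1". The footnote to Table 14.1.6 repeats this with no exception for level D: "Treatment Compliance [%] = Total IP Administration [sachets] / Dose Level [sachet/day] / Treatment Duration [days] * 100".

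The SAP's dose-level key (section 4, Instructions, item 2) describes the added cohort as "D (1 sachet/day): Careseng 1370 1 sachet before breakfast on 1st, 3rd and 5th days (modified cohort".

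Compliance decides who is evaluable. SAP 1.2 states: "For maximal tolerated dose (MTD) determination, a MTD-Evaluable Population is defined as below". For a DLT-free level D volunteer the condition is that he or she "completes DLT observation period with 100% of study drug compliance (level D"), which matches protocol 3.1. The same population is restated in item 3 of those Instructions and again in the Instructions to the subject data listings, for all levels alike, as "Experiences DLT OR with at least 80% of study drug compliance and has exposed to Careseng 1370 for at least 4 days". Both restatements omit the level D branch and the requirement to complete the DLT observation period.

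**The concern.** The SAP formula assumes dosing on every day between the first and last dose. That is true of levels A, B and C, but level D is dosed on alternate days under a daily-rate label. Perfect adherence therefore cannot reach 100%, and 100% is exactly what SAP 1.2 requires there. The volunteers removed would be the adherent ones without a DLT, who should form most of the denominator of the DLT proportion. The population meant for the MTD would then be unusable at the lowest dose level.

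There are two further problems. One population has two different rules within the SAP, so the programmer has to choose between them. And because the calendar span ends at the last dose actually taken, whole days missed at the end drop out of the denominator at every level.

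**Working it through.** **Inputs.** The schedules (protocol 5.2) give planned totals of A 5, B 10, C 15 and D 3 sachets. The SAP's labelled daily doses are A 1, B 2, C 3 and D 1. The thresholds are 100% for level D in SAP 1.2, and 80% with at least 4 days' exposure in the restatements.

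**Formulas.** Protocol: sachets taken / planned total. SAP: sachets taken / (daily dose × (last − first dosing day + 1)).

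**Full adherence.** The protocol formula gives 100% at every level, including 3/3 at D. The SAP formula gives A 5/(1 × 5), B 10/(2 × 5) and C 15/(3 × 5), all 100%, but D 3/(1 × 5) = 60%. That fails both thresholds and falls in the 60 to <80% band of Table 14.1.6. A rate of 0.6 sachet/day, or a duration counted as 3 dosing days, would restore 100%, and a rate of 0.5 would give 120%. None of these is in the SAP.

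**Level D patterns with the first dose on Day 1.**

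| Days taken | Protocol | SAP |
|---|---|---|
| 1, 3, 5 | 3/3 = 100% | 3/5 = 60% |
| 1, 5 | 2/3 = 66.7% | 2/5 = 40% |
| 1, 3 | 2/3 = 66.7% | 2/3 = 66.7% |
| 1 only | 1/3 = 33.3% | 1/1 = 100% |

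The only pattern that scores 100% under the SAP is a single dose, and protocol 4.3 withdraws a level D volunteer who misses any dose.

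**Effect on the DLT proportion.** Illustration: 6 treated at level D, with every DLT-free volunteer fully adherent.

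| DLTs | ITT | MTD-Evaluable under the SAP |
|---|---|---|
| 0 | 0/6 = 0% | empty |
| 1 | 1/6 = 16.7% | 1/1 = 100% |
| 2 | 2/6 = 33.3% | 2/2 = 100% |

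**The restatements after the formula is corrected.** An adherent level D volunteer has 3 dosing days over a calendar span of 5. If 4 days' exposure means dosing days, that volunteer still fails; if it means calendar span, the volunteer passes. The SAP does not say which.

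**Levels A to C, percentage reported.** A volunteer who takes every dose and stops after Day 1, 2, 3 or 4 scores 20, 40, 60 or 80% by the protocol and 100% by the SAP. Missing only the Day 5 lunch dose is not hidden: B 9/10 = 90% and C 13/15 = 86.7% under both.

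**Levels A to C, evaluability.** I counted every pattern of daily sachet counts with the first dose on Day 1 and at least 4 dosing days, applying the 80% threshold. Status changes in 0 of 5 patterns at A, 4 of 96 at B and 14 of 567 at C. All changes have the last dose on Day 4:

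- B: 7 sachets, from 7/10 = 70% to 7/8 = 87.5% (4 patterns).
- C: 10 sachets, from 10/15 = 66.7% to 10/12 = 83.3% (10 patterns); 11 sachets, from 11/15 = 73.3% to 11/12 = 91.7% (4 patterns).

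If 4 days means calendar span, the denominators at B and C become 144 and 720 and the 4 and 14 changes stay the same. These are counts of patterns, not probabilities.

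**The case against.** Level D is contingent: it opens only on de-escalation from level A, and the documents do not show that it was used. The SAP is dated 08-SEP-2022, after the last subject was expected to finish in March 2022. Dose decisions belong to the DSMB, using evaluability as the protocol defines it, and the primary endpoint is analysed in ITT. DLT counts do not change, because a volunteer with a DLT is evaluable under every version; with 2 DLTs the lowest-level conclusion is the same for 2/6 and 2/2. All of this stands and limits the finding to reporting.

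The distortion would also be visible. The DLT tables carry the note "Repeat Population only when the two populations are not identical", so the ITT version would print. Tables 14.1.1 and 14.1.2 count non-evaluable volunteers with reasons, and listings 16.2.3.2 and 16.2.6.2 show exclusions and drug accountability. This stands too, but visibility does not make the set usable.

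For levels A to C, compliance up to the last dose is a recognisable choice, and the SAP declares the change. A planned-total denominator gives a low score to someone who stopped after Day 2 as protocol 4.3 directs (40%). That is a fair reason to keep the SAP's measure as a second, labelled row. It is not a reason to let it decide evaluability. Total IP Administration, Treatment Duration and the last treatment date in listing 16.2.1.2 still reveal an early stop.

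The restatements may be shorthand for SAP 1.2. Even so, they state a different rule, and nothing says which one governs.

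**Conclusion.** The concern holds. As written, a level D volunteer who takes every sachet scores 60%, and without a DLT is excluded under every version of the MTD-Evaluable definition. If level D opens, that set contains essentially only volunteers with a DLT: its DLT proportion is 100% if any DLT occurs, and the set is empty if none does. This follows from the SAP's own text; only the cohort of 6 with full adherence is illustrative. That the restatements would still exclude level D after the formula is corrected depends on reading exposure as dosing days.

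In levels A to C the consequence is a compliance percentage, and a mean daily dose, that do not reflect an early stop. Evaluability is almost unchanged there, because protocol 4.3 withdrawals and the completion rule in SAP 1.2 should catch most of the affected cases. DSMB decisions, DLT counts and the ITT primary endpoint are unaffected. It should be fixed, since the SAP itself specifies level D columns and a set for the MTD.

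**What to change.** - In SAP 1.3, Table 14.1.6 and listing 16.2.6.1, compute compliance as sachets taken divided by the planned total under the documented schedules: A 5, B 10, C 15, D 3. A fully adherent level D volunteer then scores 3/3 = 100%, and levels A to C stay at 100% for full adherence.
- Keep treatment duration and mean daily dose as descriptive rows. If compliance up to the last dose is wanted, add it as a separately labelled row that is not used for evaluability.
- Label level D by its documented schedule (1 sachet on Days 1, 3 and 5), so that its column heading differs from level A's.
- Replace both restated MTD-Evaluable definitions with the SAP 1.2 and protocol 3.1 definition, including the level D branch and completion of the DLT observation period. State whether 4 days' exposure counts dosing days or calendar span.

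The cost is SAP wording, one derived variable, one column label and two definitions. No new data are needed.
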